4.3 Withdrawal of Subjects from Study

Subjects **must be withdrawn from the trial** (treatment and procedures) for the following reasons:

- Subject withdraws consent from study treatment and study procedures. A subject must be removed from the trial at his/her own request or at the request of his/her legally acceptable representative. At any time during the trial and without giving reasons, a subject may decline to participate further. The subject will not suffer any disadvantage as a result.
- Pregnancy. Pregnancies will be reported to Taiho within 24 hours of having knowledge of the event. Pregnancy will not be reported as an SAE but the subject must be withdrawn from the trial immediately. (Note: subjects who have been withdrawn from treatment with study drug because of pregnancy should not undergo CT scans [with contrast]/MRI or bone scans while pregnant.)
- If, in the investigator's opinion, continuation of the trial would be harmful to the subject's well-being.
- Subject is lost to follow-up.
- Death.

All subjects who discontinue should comply with protocol specified follow-up and survival procedures. The ONLY exception to this requirement is when a subject withdraws consent for all

study procedures or loses the ability to consent freely (i.e., is imprisoned or involuntarily incarcerated for the treatment of either a psychiatric or physical illness). If a subject was withdrawn before completing the study, the reason for withdrawal must be entered on the appropriate case report form page.

Subjects **may be** withdrawn from study treatment for the following reasons:

- The subject is non-compliant with TAS 102 administration, ramucirumab administration, or trial procedures; including the use of anti-cancer therapy not prescribed by the study protocol.
- Severe allergic reaction to TAS 102 or ramucirumab.
- The development of a second cancer.
- Development of an illness or situation which would, in the judgment of the investigator, significantly affect assessments of clinical status and trial endpoints.
- Deterioration of ECOG performance status to 3 or 4.
- Use of illicit drugs or other substances that may, in the opinion of the investigator, have a reasonable chance of contributing to toxicity or otherwise skewing trial result.

Any subject removed from the trial will remain under medical supervision until discharge or transfer is medically acceptable.

Any subject with progression of disease will come off of treatment except for patients deriving clinical benefit as deemed by the principal investigator with a maximum of 24 months on therapy. In all cases, the reason for withdrawal must be recorded in the CRF and in the subject's medical records.

4.3.1 Screen Failures/Dropouts/Replacements

A subject who discontinues study participation prematurely for any reasons except death, disease progression and severe toxicity is defined as a dropout.

A subject who, for any reason (e.g., failure to satisfy the selection criteria), terminates the study before the time point used for the definition of "dropout" (see above) is regarded a "screening failure".

Subjects who withdraw from treatment (for any reason) may be replaced.

4.3.2 Patient Replacement

Dropout (see 4.3.1 for definition of "dropout") patients will need to be replaced.

Patients will be replaced if they come off treatment without any response evaluation for reasons other than drug related AE or disease progression.

5. Treatment Plan

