9.2 Determination of sample size

The primary objective of this study is overall survival at 6 months. Overall survival (OS) will be defined as the time from starting on trial to date of death due to any cause. Dropouts/screen failures defined in section 4.3.1. Patients will be considered inevaluable for the primary endpoint of 6 months of overall survival if they are not able to complete first cycle or if they are lost follow-up prior to 6 months from starting on trial except death. Inevaluable patients will be replaced. The study will test the null hypothesis of $\leq 45\%$ of OS at 6 month against the alternative of $\geq 70\%$ of OS at 6 month. The sample size was determined based on the Simon's two-stage minimax design. With one-sided 10% of type I error rate and 90% power, a sample of evaluable 25 patients will be evaluated; 15 in first stage and additional 10 patients in second stage. If 7 or more out of 15 survive 6 months or more, the study goes on the second stage. The experimental treatment will be deemed to have good activity if ≥ 15 out of 25 patients survive 6 months or more. We will continue to recruit patients during interim analysis

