9.3 Statistical analysis

Overall survival (OS) is defined as the time from starting on trial to date of death due to any cause and progression-free survival (PFS) is defined as the duration of time from start of treatment to time of progression or death, whichever comes first. The final analysis will be conducted after the follow-time of the last patient exceeds 6 months. The primary endpoint of the study is OS at 6 month. The experimental treatment will be deemed to have good activity if ≥ 15 out of 25 evaluable patients survive 6 months or more. OS will be estimated using the Kaplan-Meier method and the two-sided 95% confidence interval (CI) for median OS will be computed using log-log transformation.

The secondary endpoints in this study include toxicity, PFS and the objective response rate (ORR) defined as (complete response (CR) + partial response (PR)) using RECIST 1.1 criteria (Appendix A). ORR will be reported with 95% CI computed by the Clopper-Pearson method. The frequency and severity of adverse events and tolerability of the regimen will be summarized using descriptive statistics. PFS with 95% CI will be estimated. As exploratory objective, the association between biomarkers and clinical outcomes (ORR, OS and PFS) will be examined using multiple logistic regression and the multivariable Cox regression model. A p-value of <0.05 will be considered statistically significant. Frequency and severity of adverse events will be summarized using descriptive statistics.

10. Data Recording

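### Sections 4.3.1/4.3.2 and 9.2 use different replacement tests, so a patient evaluable for 6-month survival can have to be replaced, and no passage says whose outcome enters the 7/15 and 15/25 counts

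*Combined protocol and SAP*

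**What the plan says.** Replacement is governed in three places.

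- **Section 4.3.1** defines the dropout: "A subject who discontinues study participation prematurely for any reasons except death, disease progression and severe toxicity is defined as a dropout". It also permits, without requiring, replacement of anyone who withdraws from treatment.
- **Section 4.3.2** says that dropout "patients will need to be replaced" and adds a second mandatory trigger: "Patients will be replaced if they come off treatment without any response evaluation for reasons other than drug related AE or disease progression". Neither trigger refers to vital status or to completion of cycle 1.
- **Section 9.2** sets evaluability for the primary endpoint. A patient is inevaluable if cycle 1 is not completed or "if they are lost follow-up prior to 6 months from starting on trial except death", and inevaluable patients are replaced.

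Section 4.3 keeps patients under observation after they stop: "All subjects who discontinue should comply with protocol specified follow-up and survival procedures". The exceptions are withdrawal of consent for all procedures and loss of the ability to consent freely.

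The decision rule is fixed. At least 7 of the first-stage 15 must survive 6 months, and under Section 9.3 success needs at least "15 out of 25 evaluable patients survive 6 months or more".

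**The concern.** The second trigger in 4.3.2 is a response-endpoint criterion, but it decides who is replaced in a trial whose primary endpoint is survival. Once cycle 1 is complete, a patient without a scan can still supply a valid 6-month outcome. Replacing that patient puts more than 25 evaluable patients in line for 25 places.

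Two things are then at stake. If the replaced patient and the replacement both count, a cut-off built for 25 outcomes is applied to more. If the replaced patient is removed, a known or knowable primary outcome is discarded. The exceptions in the second trigger do not include death as such, so what is discarded may be a failure. If the choice is left to the analysis, it can be made with outcomes in hand.

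**Working it through.** **1. Where the two rules part.** Section 3 places the first response evaluation after 2 cycles (2 × 28 = day 56). Calendar note c places it after every 3 cycles (about 3 × 28 = day 84). Cycle 1 ends at day 28. Two kinds of patient fall between day 28 and the first scan:

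- One stops by choice in week 6, has no scan and stays in survival follow-up. Under 9.2 this patient is evaluable; under 4.3.2 the patient must be replaced.
- One dies in that window from a cause that is neither drug-related nor documented progression. Section 4.3 lists death as a reason for withdrawal. Under 9.2 this is an evaluable failure. The patient is not a dropout, because 4.3.1 excepts death, but read literally the second trigger in 4.3.2 still requires replacement.

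**2. The plan's own figures.** Section 9.2 says "The sample size was determined based on the Simon's two-stage minimax design", and continues "With one-sided 10% of type I error rate and 90% power". The inputs are p0 = 0.45, p1 = 0.70, 15 + 10 patients and cut-offs 7 and 15. The exact probability of success with n outcomes in total is

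P(success) = Σ over x = 7 to 15 of Bin(x; 15, p) × P[Bin(n − 15, p) ≥ 15 − x].

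At n = 25 this gives 0.0951 for p = 0.45 and 0.9004 for p = 0.70. The stated design reproduces, with about half a percentage point to spare on the type I error.

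**3. Replaced patient and replacement both counted, cut-off still 15.** The same sum with the extra outcomes in stage 2:

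| Outcomes counted | Type I error | Power |
|---|---|---|
| 25 | 0.0951 | 0.9004 |
| 26 | 0.1318 | 0.9357 |
| 27 | 0.1735 | 0.9575 |
| 28 | 0.2180 | 0.9703 |

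With the extra outcomes in stage 1 and the first cut-off still 7, the type I error is 0.1342, 0.1808 and 0.2341 for one, two and three extras.

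**4. Exactly 25 counted, chosen freely from 26.** Whenever the 26 contain at least 15 survivors and at least one failure, leaving out a failure gives at least 15 of 25. An unrestricted choice made with outcomes known can therefore reach the same 0.1318.

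**5. Exactly 25 counted, replaced early deaths dropped.** Let q be the share of all patients who are early deaths removed in this way. Survival among those retained under the null becomes 0.45/(1 − q), which goes into the formula at n = 25:

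- q = 2%: 0.45/0.98 = 0.459, type I error 0.112
- q = 5%: 0.45/0.95 = 0.474, type I error 0.142
- q = 10%: 0.45/0.90 = 0.500, type I error 0.210

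This supposes that only deaths are removed. Removing future survivors as well would offset part of it.

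**6. Exactly 25 counted, replacement unrelated to survival.** The rate stays at 0.45 and the type I error at 0.0951.

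The documents give neither the number of replacements nor q.

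**The case against.** The strongest reply is that the plan already fixes the denominator. Sections 9.2 and 9.3 speak of 25 evaluable patients, and replacing normally means substituting, not adding. A reader might infer from 4.3.2 that the type I error does exceed 10%. The documents do not support that: no passage says that more than 25 are counted, and step 6 gives 9.5% when replacement is unrelated to survival. This stands, so the excess is conditional. It does not say who fills the 25 places, because the replaced patient and the replacement both meet the 9.2 definition.

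Second, the affected group is narrow. Section 6.7 and calendar note n provide for imaging at the end-of-treatment visit if none was done in the previous 4 weeks, so a week-6 stopper may have a response evaluation after all. That also stands, but the imaging in 6.7 is optional, and a patient who dies cannot attend the visit. In addition, leaving the study before month 6 will often mean loss to follow-up, which 9.2 already covers. The dropout trigger therefore adds less than the no-evaluation trigger. Nor is 6-month status usually known when the replacement is made; it becomes known later.

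Third, because 4.3.2 has no time limit, a reader might infer that someone alive at month 6 who leaves at month 9 must be replaced and removed, at a cost in power. That is a strained reading, since such a patient has already supplied the primary outcome. It would also lower the type I error: if 10% or 20% of survivors were removed, 0.45 becomes 0.45 × 0.90/(1 − 0.045) = 0.424 or 0.45 × 0.80/(1 − 0.09) = 0.396, and the error falls to 0.058 or 0.031. The point does not rest on this case.

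**Conclusion.** The conflict between 4.3.2 and 9.2 is in the text, and following both literally leaves the composition of the 25 undefined. Whether the error rate suffers depends on how the gap is filled: one doubly counted patient is enough to pass 10%, and so are dropped early deaths at 2% of patients, the smallest share examined. Random substitution within 25 does no harm. The numbers of extra outcomes and the shares of early deaths are assumptions used to show scale; they are not predictions, and the group concerned may be small. In a single-arm trial decided by one count against 15, the ambiguity should be removed before any patient is replaced.

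**What to change.** - For the primary endpoint, use one replacement definition, that of Section 9.2.
- In 4.3.1 and 4.3.2, state that the dropout trigger, the trigger for missing response evaluation and the optional replacement after treatment withdrawal do not apply to a patient who is evaluable under 9.2, and that a death before 6 months in such a patient is kept as a failure.
- In 9.2 and 9.3, state that the 7/15 and 15/25 rules use the first 15 and the first 25 evaluable patients in order of enrollment.

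This leaves the cycle 1 clause of 9.2 as written, so it creates no new contradiction; the merit of that clause is a separate question. If the sponsor prefers to count every evaluable patient, the final cut-off must be given for each possible total. For example, a cut-off of 16 gives type I error 0.067 and power 0.873 with 26 outcomes, and 0.096 and 0.917 with 27.

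The cost is protocol wording, and enrollment would tend to fall. The small downside is that a few patients without a scan stay among the 25, so the response rate rests on slightly fewer scanned patients.

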5.1 Drug Administration

Ramucirumab

Ramucirumab is provided as a liquid solution at a concentration of 10mg/ml in either 100mg (10ml) or 500mg (50ml) single dose vials. The drug product is stored as a liquid solution in a refrigerator at 2°C to 8°C until time of use. Ramucirumab is a sterile, preservative-free, clear to slightly opalescent and colorless to slightly yellow solution for intravenous infusion following dilution and preparation. After withdrawal of the required volume of ramucirumab from the vials, it can be further diluted with only 0.9% sodium chloride in an intravenous infusion container to a final volume of 250ml. The diluted ramucirumab can be administered via infusion pump over 60 minutes (\pm 15minutes) through a separate infusion line. When patients develop infusion reaction, we will follow 5.1.1.2.1 infusion related reaction management. The diluted ramucirumab solutions may be stored at room temperature for up to 4 hours or at 2 to 8°C for up to 24 hours.

TAS 102

TAS 102 should be administered orally twice a day within 1 hour of completion of morning and evening meals on Days 1 through 5 and Days 8 through 12 of each 28-day cycle. The tablets should be swallowed whole with water and should not be broken, or chewed.

TAS-102 15 mg/7.065 mg (trifluridine/tipiracil hydrochloride) and 20 mg/9.42 mg (trifluridine/tipiracil hydrochloride) film coated tablets. The film coated tablets can be printed or unprinted.

TAS 102 tablets are supplied in a blister card containing 20, 40 or 60 tablets. Keep TAS 102 out of the sight and reach of children.

TAS 102 should be stored according to the storage conditions indicated on the label. The recommended storage condition for TAS 102 is 15°C to 23°C (59°F to 86°F). Each patient will enter daily use of TAS 102 in a medication diary (Appendix B) for a measure of compliance. A dairy card will be issued and returned at each cycle.

Treatment

Treatment will be administered on an outpatient basis. Reported AEs and potential risks are described in Section 8. Dose delays for TAS 102 and ramucirumab are described in Section 5.1.6. No investigational or commercial agents or therapies other than those described below may be administered with the intent to treat the patient's malignancy. The dose of TAS is 35mg/m² (trifluridine dose) twice a day, taken orally. The dose of ramucirumab is 8mg/kg IV every 2 weeks. Each cycle will last for 4 weeks.

Arm	Ramucirumab Dose	TAS 102*
1	8 mg/kg q2wk	35mg/m ² BID

*To be given PO on days 1-5 and 8-12 of every 28 day cycle

TAS102 (35mg/m²) twice a day was safely administered with anti-VEGF therapy (bevacizumab)

in a recent a phase 1/2 study⁴⁴. Based on the data, each subject will receive TAS 102 35mg/m² twice a day and ramucirumab 8mg/kg Q2W continuously. Since unexpected toxicities can occur with this combination, we will closely monitor first 6 patients for first 28 days. If none or one of these patients has a dose limiting toxicity, we will continue without dose adjustment. If ≥ 2 patients has a dose limiting toxicity, the dose will be decreased to level -1 (TAS 102: 30mg/m² twice a day and ramucirumab: 8mg/kg Q2W, details in table 1), and 6 additional patients will be enrolled at dose level -1. If none or one of these patients has a dose limiting toxicity at dose level -1 for first 28 days, we will use dose level -1. If ≥ 2 patients has a dose limiting toxicity at dose level -1, the study will be terminated. First 6 or 12 patients depending on dose limiting toxicities will be used for primary and secondary objectives. Dose limiting toxicity is defined as a grade 3 or higher non-hematological toxicity excluding controllable nausea, vomiting, hypertension, diarrhea, transient electrolyte abnormalities and alopecia; grade 4 neutropenia lasting 7 days or more; grade 3 or higher febrile neutropenia; grade 4 thrombocytopenia.

5.1.1 Management (dose Modifications and dose delays) for Treatment-Related Toxicity

All toxicities will be graded according to National Cancer Institute's (NCI's) Common Terminology Criteria for Adverse Events (CTCAE) (NCI CTCAE v 5). The study investigator will determine if either or both medications should be held.

Dose reductions for AEs related to TAS 102 are permitted dose reductions to a minimum dose of 20mg/m² twice a day in 5mg/m² steps. After dose reduction, escalation of dose is not allowed.

Table 1. TAS 102 dose modifications

TAS 102 dose (BID)	BSA (m ²)*	Dosage in mg (BID)	Total daily dose (mg)	Tablets per dose	
				15mg	20mg
Starting dose					
35mg/m ²	<1.07	35	70	1	1
	1.07-1.22	40	80	0	2
	1.23-1.37	45	90	3	0
	1.38-1.52	50	100	2	1
	1.53-1.68	55	110	1	2
	1.69-1.83	60	120	0	3
	1.84-1.98	65	130	3	1
	1.99-2.14	70	140	2	2
	2.15-2.29	75	150	1	3
	≥ 2.30	80	160	0	4
Level 1 dose reduction: from 35mg/m ² to 30mg/m ²					
30mg/m ²	<1.09	30	60	2	0
	1.09-1.24	35	70	1	1
	1.25-1.39	40	80	0	2
	1.4-1.54	45	90	3	0
	1.55-1.69	50	100	2	1

	1.70-1.94	55	110	1	2
	1.95-2.09	60	120	0	3
	2.10-2.28	65	130	3	1
	≥ 2.29	70	140	2	2
Level 2 dose reduction: from 30mg/m ² to 25mg/m ²					
25mg/m ²	<1.10	25	50	2 (PM)¶	1 (AM)¶
	1.10-1.29	30	60	2	0
	1.30-1.49	35	70	1	1
	1.50-1.69	40	80	0	2
	1.70-1.89	45	90	3	0
	1.90-2.09	50	100	2	1
	2.09-2.29	55	110	1	2
	≥ 2.30	60	120	0	3
Level 3 dose reduction: from 25mg/m ² to 20mg/m ²					
20mg/m ²	<1.14	20	40	0	1
	1.14-1.34	25	50	2 (PM)¶	1 (AM)¶
	1.35-1.59	30	60	2	0
	1.60-1.94	35	70	1	1
	1.95-2.09	40	80	0	2
	2.10-2.29	45	90	3	0
	≥ 2.29	50	100	2	1

* Calculate BSA to 2 decimal places.

¶ At a total daily dose of 50mg, patients should take 1 x 20mg tablet in the morning and 2 x 15mg tablets in the evening.

Dose reductions of ramucirumab will be allowed only for proteinuria with 6 mg/kg for first episode of proteinuria (> 2 g/24 hours) and with 5 mg/kg for second episode of proteinuria (> 2 g/24 hours). Only dose delay will be allowed for the other AEs related to ramucirumab.

Table 2. Ramucirumab dose modifications

Starting dose	8mg/kg
Level 1 dose reduction	6mg/kg
Level 2 dose reduction	5mg/kg

Dose modifications will not be required for AEs that are clearly not attributed to TAS 102 or ramucirumab (such as an accident) or for laboratory abnormalities that are not deemed to be clinically significant.

If a subject experiences a clinically significant and/or unacceptable toxicity, dosing will be interrupted and supportive therapy administered as required.

5.1.1.1 Management for Treatment-Related Toxicity of TAS 102

5.1.1.1.1 Non-hematologic toxicities of TAS 102

Table 3. Non-hematologic toxicity management

Grade¶	Dose hold/resumption within a 28-day treatment cycle	Dose adjustment for next cycle
Grade 1 or 2		
Any occurrence	Maintain treatment at the same dose level	None
Grade 3* or higher		
1 st , 2 nd or 3 rd occurrence	Suspend treatment until Grade 0 or 1	Reduce by 1 dose level from the previous level
4 th occurrence	Discontinue treatment	Discontinue treatment

¶ At the discretion of the investigator, patients may continue on study medication at the same dose without reduction or interruption for AEs (irrespective of grade) considered unlikely to become serious or life-threatening (including, but not limited to, fatigue, alopecia, changes in libido, and dry skin).

* Except for grade 3 nausea and/or vomiting controlled by antiemetic therapy or diarrhea responsive to antidiarrheal medication. Moreover, if grade 4 non-hematotoxicity that is related to the protocol therapy is observed, protocol therapy is to be discontinued. However, in case of adverse events, which can clearly be judged to have derived from the primary disease, depending on the judgement of the investigator (subinvestigator) protocol therapy can be continued. In this case, the reason for this judgement must be recorded in the medical records, etc. (For example: Grade 3 cancer pain that is associated with the primary disease, Grade 3 weight loss that is associated with the primary disease, etc.)

5.1.1.1.2 Hematologic toxicities of TAS 102

Criteria for dose hold and resumption in response to hematologic toxicities related to myelosuppression are described in Table 2.

Uncomplicated neutropenia or thrombocytopenia \leq grade 3 does not require a reduction in dose of study medication. Patients who experience uncomplicated Grade 4 neutropenia or thrombocytopenia that results in a >1 week delay of the start of the next cycle should start the next cycle with dose reduction in $5\text{mg}/\text{m}^2$ step. If toxicity remains despite 4 dose reductions or at a minimum dose ($15\text{mg}/\text{m}^2$ twice a day), discontinue TAS 102.

Table 4. Hematologic toxicity management

Parameter	Hold Criteria		Resumption Criteria*	Dose adjustment for next cycle
	Conventional Units	SI units		
Neutrophils	<500/mm ³	<0.5x10 ⁹ /L	≥1500/mm ³ (IU: ≥1.5x10 ⁹ /L)	Details below¶
Platelets	<50,000/mm ³	<50x10 ⁹ /L	≥75,000/mm ³ (IU: ≥75x10 ⁹ /L)	Details below¶

* These resumption criteria apply to the start of the next cycle for all patients regardless of whether or not the hold criteria were met. Both conventional and SI (International System) units are presented in CTCAE v. 5.

¶ 1) ≤ Grade 3 neutropenia or thrombocytopenia

- If there are no complications (such as fever, infection or hemorrhage), there is no need to reduce the dose of TAS 102
- If there are complications, the necessity of reducing dose should be considered also with regard to safety.
- For neutropenia, pegfilgrastim or filgrastim can be administered at investigator's discretion.

2) Grade 4 neutropenia or thrombocytopenia

- When there are no complications, but initiation of the next cycle is delayed by more than one week, dose should be reduced by 1 level (Table 1) when starting next cycle (dose is not reduced when administered on the same weekday). If initiation is not delayed by more than one week, the next cycle can be initiated at the same dose level.
- If there are complications, in consideration of the safety of the patient, dose should be reduced by 1 level (Table 1) when starting the next cycle.
- For neutropenia, pegfilgrastim or filgrastim can be administered at investigator's discretion.

5.1.1.1.3 Dose resumption timing of TAS 102

If the patient recovers from the toxicities to the resumption criteria defined above during the 2-week treatment period (treatment Days 1 through 5, 8 through 12), and no dose reduction is required, study drug therapy may be resumed during that cycle.

If a dose reduction is required, study drug therapy should be resumed at the start of the next cycle at the appropriate dose level according to instructions provided in Table 1 and 2. If the study drug dose is reduced, it must not be increased for subsequent cycles.

If the toxicities that are defined above recover during the recovery period (Days 13 through 28), start the next cycle on schedule at the appropriate dose level according to instructions provided in Table 1, 3 and 4.

If the toxicities that are defined above do not recover during the treatment or rest period, the start of the next cycle can be delayed for a maximum of 28 days from the scheduled start date of the next cycle. If resumption criteria are met by this maximum 28-day delay, start the next cycle at the appropriate dose level according to instructions provided in Table 1, 3 and 4. Patients who

require more than a 28-day delay in the scheduled start date of the next cycle will have study medication discontinued.

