5.1.1.2 Management for Treatment-Related Toxicity of ramucirumab

Adverse events of concern which may be related with ramucirumab include are infusion-related reactions, hypertension, arterial or venous thromboembolic events, bleeding (hemorrhagic) events, proteinuria, cardiac events, gastrointestinal perforation, anemia, surgery and wound healing liver injury/liver failure, and reversible posterior leukoencephalopathy syndrome (RPLS). Listed below are guidelines on how to manage these toxicities. Dose reductions of ramucirumab will be allowed only for proteinuria with 6 mg/kg for first episode of proteinuria (2-3 g/24 hours) and with 5 mg/kg for second episode of proteinuria (2-3 g/24 hours) (details on table 2 and **5.1.1.2.4**). Only dose delay will be allowed for the other AEs related to ramucirumab.

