5.1.1.2.4 Proteinuria

If, while on ramucirumab, a patient has proteinuria $\geq 2+$ per a dipstick or routine urinalysis test, ramucirumab will continue as scheduled, and a 24-hour urine collection will be conducted prior to the subsequent scheduled treatment in 2 weeks.

- The following are treatment guidelines for ramucirumab related proteinuria

Proteinuria	Management
< 2g/24hours urine	
 Continue on ramucirumab at the same dose without interruption
2-3g/24hours urine (first episode)	
 Hold ramucirumab for 2 weeks Repeat a 24-hour urine collection prior to next infusion. Resume ramucirumab at a reduced dose level (6 mg/kg every 2 weeks) once the protein level returns to < 2 g/24 hours.
2-3g/24hours urine (second episode)	
 Hold ramucirumab for 2 weeks Repeat a 24-hour urine collection prior to next infusion. Resume ramucirumab at a reduced dose level (5 mg/kg every 2 weeks) once the protein level returns to < 2 g/24 hours.
2-3g/24hours urine (third episode) or >3g/24hours urine	
 Discontinue ramucirumab

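### Dose-modification rules contradict each other at the TAS 102 floor (20 or 15 mg/m² twice daily) and for a first or second proteinuria episode above 3 g/24 h (reduce or stop ramucirumab)

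*Combined protocol and SAP*

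**What the plan says.** **TAS 102.** Section 5.1.1 gives the general rule: "Dose reductions for AEs related to TAS 102 are permitted dose reductions to a minimum dose of 20mg/m² twice a day in 5mg/m² steps". Table 1 lists 35, 30, 25 and 20 mg/m² and nothing lower. For hematologic toxicity, 5.1.1.1.2 sets a different stopping point. It begins "If toxicity remains despite 4 dose reductions or at a minimum dose", gives that minimum in parentheses as 15 mg/m² twice daily, and then says to discontinue. For uncomplicated grade 4 events that delay the next cycle by more than a week, the notes to Table 4 say "dose should be reduced by 1 level (Table 1) when starting next cycle"; a complicated grade 4 event also costs one Table 1 level. For non-hematologic grade 3 or higher events, Table 3 says "Reduce by 1 dose level from the previous level" for the first three occurrences and stops treatment at the fourth. Under section 5.1, if two or more of the first six patients have a dose-limiting toxicity, "the dose will be decreased to level -1", which is 30 mg/m².

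**Ramucirumab and proteinuria.** Section 5.1.1 says "Dose reductions of ramucirumab will be allowed only for proteinuria with 6 mg/kg for first episode of proteinuria (> 2 g/24 hours", then 5 mg/kg for a second episode at the same threshold, with no upper limit. Section 5.1.1.2 puts a ceiling on the same reductions: "6 mg/kg for first episode of proteinuria (2-3 g/24 hours", and likewise for the second episode. In 5.1.1.2.4, the row "2-3g/24hours urine (third episode) or >3g/24hours urine" carries the instruction to discontinue ramucirumab.

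**The concern.** Both conflicts are between operative instructions in the current text, and each gives two answers for one patient.

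- **TAS 102.** A patient at 20 mg/m² with a qualifying grade 4 hematologic event has no lower level under 5.1.1 and Table 1. By the wording of 5.1.1.1.2, that patient has not yet reached the point of discontinuation. The risk is a further cycle at a dose the protocol does not define.
- **Ramucirumab.** A patient with a first or second episode above 3 g/24 h gets a reduced dose under 5.1.1 and permanent discontinuation under 5.1.1.2.4. This is the more safety-relevant of the two.

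The protocol states no rule for which section prevails, and sections 10.3 and 11.1 require strict adherence to the text.

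**Working it through.** **1. TAS 102 dose ladder** (start and level -1 from section 5.1, steps from 5.1.1).

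| Start | Reductions to 20 mg/m² | Reductions to 15 mg/m² |
|---|---|---|
| 35 mg/m² | (35 − 20)/5 = 3 | (35 − 15)/5 = 4 |
| 30 mg/m² (level -1) | (30 − 20)/5 = 2 | (30 − 15)/5 = 3 |

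The two floors differ by one full level. From 35 mg/m², Table 3's three reductions end at 20 mg/m², which agrees with 5.1.1 if all reductions are non-hematologic. From level -1, Table 3's third reduction gives 15 mg/m², below the 5.1.1 floor.

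**2. Proteinuria, side by side (first or second episode).**

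| 24-hour protein | 5.1.1 | 5.1.1.2 | 5.1.1.2.4 |
|---|---|---|---|
| 2-3 g | reduce (above 2 g) | reduce | hold, then reduce |
| above 3 g | reduce | no reduction provided for | discontinue |

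The reduced doses are 6/8 = 75% and 5/8 = 62.5% of the starting dose.

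**3. Earliest time of the TAS 102 conflict.** From 35 mg/m² it takes three reductions and then a fourth toxicity, so the decision falls at the start of cycle 5: 4 × 28 = day 112 without delays, or 4 × (28 + 8) = day 144 with an 8-day delay after each cycle. From level -1 it is 3 × 28 = day 84 to 3 × 36 = day 108.

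Assume exponential PFS with the 2.9-month median cited in section 1.4 for TAS 102 alone in gastric cancer (88.3 days), S(t) = 0.5^(t/88.3):

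- From 35 mg/m²: S(112) = 0.415 and S(144) = 0.323, so about 10 to 8 of 25 are still progression-free.
- From level -1: S(84) = 0.517 and S(108) = 0.428, so about 10 to 8 of the 25 − 6 = 19 patients after the first six.

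These counts describe who could still be on treatment. Only some of them would be at 20 mg/m² with new toxicity.

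**4. How many might reach the TAS 102 conflict.** The documents give no dose-reduction rate. Assume a constant chance q per 28-day cycle of a toxicity that triggers a reduction, with time on treatment following the same 2.9-month median. The chance of staying on treatment per cycle is s = 0.5^((28/30.4375)/2.9) = 0.8026. With no limit on cycles, the chance of a fourth trigger is s³ × [q/(1 − s(1 − q))]⁴. For q = 20% this is 0.517 × (0.2/0.3579)⁴ = 0.0504. Capping treatment at 26 cycles (about 24 months) gives:

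| q per cycle | P(4th trigger), 35 mg/m² start | Expected of 25 | P(3rd trigger), level -1 start | Expected of 19 |
|---|---|---|---|---|
| 5% | 0.0009 | 0.02 | 0.0058 | 0.11 |
| 10% | 0.0083 | 0.21 | 0.0297 | 0.56 |
| 20% | 0.0501 | 1.25 | 0.1123 | 2.13 |
| 34% | 0.1412 | 3.53 | 0.2434 | 4.62 |

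The 34% row is deliberately extreme. It borrows the grade 3 or higher neutropenia figure in section 1.4, which is a cumulative rate. Uncomplicated neutropenia requires a reduction only at grade 4 with more than a week's delay, so the true q should be well below it.

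**5. Patient-level range.** If a fraction q of patients meets either conflict, the expected number is 25q and P(at least one) = 1 − (1 − q)²⁵.

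- q = 1%: 0.25 patients, 0.222
- q = 2%: 0.5 patients, 0.397
- q = 5%: 1.25 patients, 0.723

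For proteinuria above 3 g/24 h alone, an assumed 1% to 10% gives 0.25 to 2.5 patients.

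**6. Table 1 bands.** Of the 30 joins between adjacent body-surface-area bands (9 + 8 + 7 + 6), 28 step by 0.01 m² and two overlap at a single value:

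- 2.09 m² at 25 mg/m²: nominal 52.25 mg, listed as 50 or 55 mg (−4% or +5%).
- 2.29 m² at 20 mg/m²: nominal 45.8 mg, listed as 45 or 50 mg (−2% or +9%).

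**7. Design check.** Exact binomial calculation of the section 9.2 rule (at least 7 of 15, then at least 15 of 25) gives type I error 0.0951 at 45% and power 0.9004 at 70%. This reproduces the stated 10% and 90%. None of it depends on the dosing rules.

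**The case against.** The best reply is that a careful reader would resolve both conflicts safely. The 5.1.1 proteinuria sentence says which reductions are permitted; it does not order continued dosing. Section 5.1.1.2 refers the reader to 5.1.1.2.4, the only place with the operating steps, where dosing resumes only after protein falls below 2 g/24 h. For TAS 102, the general floor, Table 1 and the Table 4 notes all point to 20 mg/m², so one sentence is the outlier. The level -1 route needs at least two dose-limiting toxicities among the first six patients, and the general floor already caps Table 3. The rates are assumed, and the trial's inference is untouched.

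Much of this stands. The proteinuria error arises only if 5.1.1 is read alone. Table 3's agreement with the 20 mg/m² floor fails if hematologic reductions have used part of the same ladder. That the affected patients are few is a judgement.

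It does not remove the conflict. No rule of precedence is stated, and neither natural one works for both drugs. Letting the specific section govern settles proteinuria safely but selects the 15 mg/m² text, which has no dosing rows. Letting the general section govern settles TAS 102 but selects the less safe proteinuria reading. Tablets come only as 15 and 20 mg and must be taken whole, so a 15 mg/m² dose would need its own table.

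**Conclusion.** The concern holds. The protocol gives contradictory instructions at the TAS 102 floor and for first or second proteinuria episodes above 3 g/24 h. The two body-surface-area overlaps are real but minor. The number affected is probably small: about one patient or fewer at the TAS 102 floor from a 35 mg/m² start for per-cycle trigger rates up to 20%, about two from level -1 at that rate, and 0.25 to 2.5 for proteinuria at 1% to 10%. All of these rest on assumed rates, exponential time on treatment and a monotherapy median. The finding itself needs no assumption, because it follows from the text. The sample size, the primary decision rule and the adverse-event summaries do not change. It should be fixed because it concerns stopping or continuing treatment, and the correction is cheap.

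**What to change.** Subject to the investigator confirming that 20 mg/m² is the intended floor:

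- **5.1.1.1.2:** replace the four-reduction and 15 mg/m² wording with a rule that toxicity remaining at 20 mg/m² twice daily (three reductions from 35, or two from level -1) means TAS 102 is discontinued.
- **Table 3:** add that no reduction goes below 20 mg/m². This covers the level -1 start and patients with mixed hematologic and non-hematologic reductions.
- **5.1.1:** change both proteinuria thresholds to 2-3 g/24 h, and state that more than 3 g/24 h means discontinuing ramucirumab per 5.1.1.2.4.
- **Table 1:** start the overlapping 25 mg/m² band at 2.10 instead of 2.09, and the last 20 mg/m² band at 2.30 instead of 2.29.

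The cost is one amendment of wording and table entries, with no added procedures, visits or patients. If 15 mg/m² was intended, the 5.1.1 floor must change instead, and Table 1 needs a further block of rows.
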